9.5. Emergency Unblinding of Treatment Assignment

In a medical emergency during the double-blind, vehicle-controlled period, if the investigator deems it necessary to determine optimal medical management of the participant, emergency unblinding will be performed exclusively by the Principal Investigator and subinvestigator as described in the IRT Study Manual. The IRT system has an option to select for "Emergency Code Break" action for a given participant. After entering the 6-digit study drug tube number and verification of the unmasking information, the investigator/subinvestigator will proceed to either final confirmation or cancellation of the code break procedure.

If a participant's treatment assignment is unblinded, the sponsor or its designee must be notified immediately by telephone followed-up with an email.

If an investigator, site personnel performing assessments, or participant is unblinded, the participant must be withdrawn from the study treatment, unless there are ethical reasons to have the participant remain on the study treatment. In these cases, the investigator must obtain specific approval from the sponsor's (or its designee's) medical monitor for the participant to continue in the study.

9.6. Pregnancy

Pregnancy, in and of itself, is not regarded as an AE unless there is suspicion that study drug may have interfered with the effectiveness of a contraceptive medication or method. When a pregnancy has been confirmed in a participant during maternal or paternal exposure to study drug, the following procedures should be followed in order to ensure safety:

- The study drug must be discontinued immediately.
- The investigator must complete and submit the Incyte Clinical Trial Pregnancy Form to the sponsor or its designee within 24 hours of learning of the pregnancy.

Data on fetal outcome are collected for regulatory reporting and drug safety evaluation. Follow-up should be conducted for each pregnancy to determine outcome, including spontaneous or voluntary termination, details of the birth, and the presence or absence of any birth defects, congenital abnormalities, or maternal and/or newborn complications, by following until the first well-baby visit. Pregnancy should be recorded on a Clinical Trial Pregnancy Form and reported by the investigator to the sponsor or its designee. Pregnancy follow-up information should be recorded on the same form and should include an assessment of the possible causal relationship to the sponsor's study drug to any pregnancy outcome, as well as follow-up to the first well-baby visit or the duration specified in local regulations, whichever is later. Refer to the Incyte Reference Guide for Completing the Clinical Trial Pregnancy Form.

Any SAE occurring during pregnancy of a study participant must be recorded on the Serious Adverse Event Report Form and submitted to the sponsor or designee.

Abnormal pregnancy outcomes (eg, spontaneous abortion, fetal death, stillbirth, congenital anomalies, or ectopic pregnancy) are considered SAEs (if occurring in the study participant) and must be reported as described in Section 9.4. If an abnormal pregnancy outcome is reported in a study participant's partner, the event should be reported to the sponsor on the Clinical Trial Pregnancy Form.

9.7. Warnings and Precautions

Special warnings or precautions for the study drug, derived from safety information collected by the sponsor or its designee, are presented in the [IB](#). Additional safety information collected between IB updates will be communicated in the form of Investigator Notifications. Any important new safety information should be discussed with the participant during the study, as necessary. If new significant risks are identified, they will be added to the ICF.

9.8. Product Complaints

The sponsor collects product complaints on study drugs and drug delivery systems used in clinical studies in order to ensure the safety of study participants, monitor quality, and facilitate process and product improvements.

All product complaints associated with material packaged, labeled, and released by the sponsor or its designee will be reported to the sponsor. All product complaints associated with other study material will be reported directly to the respective manufacturer.

The investigator or his/her designee is responsible for reporting a complete description of the product complaint via email or other written communication to the sponsor contact or respective manufacturer as noted in the packaging information. Any AE associated with a product complaint should be recorded as described in Section 9.3.

If the investigator is asked to return the product for investigation, he/she will return a copy of the product complaint communication with the product.

9.9. Treatment of Overdose

There has been no clinical experience with overdose of ruxolitinib cream. Treatment of overdose should consist of general supportive measures.

10. STATISTICS

10.1. Sample Size Determination

Approximately 300 participants will be randomized 2:1 to ruxolitinib cream 1.5% BID or vehicle and stratified by baseline skin type (Fitzpatrick scale Type I and II vs Type III, IV, V, and VI) and region (North America or Europe). The sample size is calculated to provide sufficient power (> 85%) to detect a difference between the 1.5% BID with the vehicle in primary and key secondary endpoints. The powers for different endpoints are provided in [Table 14](#). The Fisher's exact test with a 2-sided alpha of 0.05 is used to provide a conservative evaluation of statistical power, and it is accurate when there is a small expected number of responders in the vehicle group.

Table 14: Powering for Primary and Key Secondary Endpoints

Endpoints	Response Rates in Ruxolitinib 1.5% BID ^a	Response Rates in Vehicle ^a	Power ^b
F-VASI75 at Week 24	20%	5%	95%
F-VASI50 at Week 24	30%	10%	95%
F-VASI90 at Week 24	10%	1%	88%
T-VASI50 at Week 24	10%	1%	88%
Vitiligo - VNS Response at Week 24	10%	1%	88%

^a Based on the results from a Phase 2, randomized, dose-ranging study (INCB18424-211).

^b Based on the Fisher's exact test with a 2-sided alpha of 0.05.

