6.3. Measures to Minimize Bias: Randomization and Blinding

All participants will be centrally assigned to study treatment using an IRT system. The system will assign in a 2:1 ratio (ruxolitinib cream 1.5% BID:vehicle), stratified by region (North America or Europe) and skin type (Fitzpatrick scale Type I and II vs Type III, IV, V, and VI). Adolescents will make up at least 10% of participants, and no more than 50% of participants will be aged greater than 40 years. The IRT will assign participant ID numbers, track participant visits, randomize participants according to the defined parameters, maintain the blinding, and manage study drug inventory. Full details will be provided in the IRT Manual. Study treatment will be dispensed at the study visits summarized in the Schedule of Activities (see [Table 3](#) and [Table 4](#)).

After the database lock for the primary analysis, the sponsor will be unblinded, but investigators and participants will still be blinded to individual treatment assignments. This is implemented to minimize bias for the Week 52 analyses. After Week 52, investigators and participants will be unblinded.

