10.3. Statistical Analyses

The Statistical Analysis Plan will be developed and finalized before database lock and will describe the details of the statistical analyses and procedures for accounting for missing data. This section is a summary of the planned statistical analyses of the primary and secondary endpoints.

The gatekeeping testing strategy for the primary and key secondary analyses will be implemented to control the overall Type I error rate, 2-sided $\alpha = 0.05$. These endpoints will be tested in a fixed sequence at 2-sided $\alpha = 0.05$ level in the following order:

- Proportion of participants achieving F-VASI75 at Week 24
- Proportion of participants achieving F-VASI50 at Week 24
- Proportion of participants achieving F-VASI90 at Week 24
- Proportion of participants achieving T-VASI50 at Week 24
- Vitiligo - VNS Response at Week 24
- Percentage change from baseline in F-BSA at Week 24

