3.2. Control of Type I Error

The gatekeeping testing strategy for the primary and key secondary analyses will be implemented to control the overall Type I error rate, 2-sided $\alpha = 0.05$. These endpoints will be tested in a fixed sequence at 2-sided $\alpha = 0.05$ level in the following order:

- Proportion of participants achieving F-VASI75 at Week 24
- Proportion of participants achieving F-VASI50 at Week 24
- Proportion of participants achieving F-VASI90 at Week 24
- Proportion of participants achieving T-VASI50 at Week 24
- Vitiligo – VNS Response at Week 24
- Percentage change from baseline in F-BSA at Week 24

The endpoint will be tested only if the primary endpoint (and the secondary endpoints in previous steps) are rejected.

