3.3. Sample Size Considerations

Approximately 300 participants will be randomized 2:1 to ruxolitinib cream 1.5% BID or vehicle and stratified by baseline skin type (Fitzpatrick scale Type I and II vs Type III, IV, V, and VI) and region (North America or Europe). The sample size is calculated to provide sufficient power ($> 85\%$) to detect a difference between the 1.5% BID with the vehicle in primary and key secondary endpoints. The powers for different endpoints are provided in [Table 2](#). The Fisher's exact test with a 2-sided alpha of 0.05 is used to provide a conservative evaluation of statistical power, and it is accurate when there is a small expected number of responders in the vehicle group.

Table 2: Powering for Primary and Key Secondary Endpoints

Endpoints	Response Rates in Ruxolitinib 1.5% BID ^a	Response Rates in Vehicle ^a	Power ^b
F-VASI75 at Week 24	20%	5%	95%
F-VASI50 at Week 24	30%	10%	95%
F-VASI90 at Week 24	10%	1%	88%
T-VASI50 at Week 24	10%	1%	88%
Vitiligo - VNS Response at Week 24	10%	1%	88%

^a Based on the results from a Phase 2, randomized, dose-ranging study (INCB18424-211).

^b Based on the Fisher's exact test with a 2-sided alpha of 0.05.

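### The stated power of more than 85% for the primary and key secondary endpoints leaves out the fixed testing sequence; taken through the sequence, power at the plan's own rates is about 76% to 82% for VNS and borderline for T-VASI50

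*Protocol*

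**What the plan says.** Section references to the protocol are to Amendment 3-US-CA.

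- **Sample size.** Protocol 10.1: "Approximately 300 participants will be randomized 2:1 to ruxolitinib cream 1.5% BID or vehicle". The aim is to "provide sufficient power (> 85%) to detect a difference between the 1.5% BID with the vehicle in primary and key secondary endpoints". SAP 3.3 repeats this.
- **Supporting table.** Protocol Table 14 and SAP Table 2 ("Powering for Primary and Key Secondary Endpoints") give one power per binary endpoint: F-VASI75 20% v 5%, 95%; F-VASI50 30% v 10%, 95%; F-VASI90, T-VASI50 and VNS each 10% v 1%, 88%. F-BSA has no row.
- **Test behind the table.** "The Fisher's exact test with a 2-sided alpha of 0.05 is used to provide a conservative evaluation of statistical power". A footnote to the power column names the same test and alpha.
- **Testing procedure.** Protocol 10.3: "These endpoints will be tested in a fixed sequence", each step at two-sided 0.05, in the order F-VASI75, F-VASI50, F-VASI90, T-VASI50, VNS, F-BSA. SAP 3.2: "The endpoint will be tested only if the primary endpoint (and the secondary endpoints in previous steps) are rejected".

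Neither document gives a power that allows for the sequence, or a correlation between endpoints.

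**The concern.** The sentence in 10.1 covers the whole family of primary and key secondary endpoints, but the figures behind it treat each endpoint as if it were the only one tested. Under the plan's own rule, T-VASI50 is not tested unless three earlier tests succeed, and VNS not unless four do. The chance of declaring a difference on a late endpoint is the chance that it and all earlier endpoints succeed, and this must be lower than its single-test power.

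VNS is the only patient-reported endpoint in the sequence, and F-BSA is the only continuous one. A reader who takes 10.1 at face value would put the chance of success on both above 85%.

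**Working it through.** **Inputs.** 300 participants at 2:1, so 200 v 100 (Protocol 10.1, 6.3). Response rates from Table 14. Fisher's exact test, two-sided 0.05 (Protocol 10.1). Order and stopping rule from Protocol 10.3 and SAP 3.2. F-VASI50, 75 and 90 are cut-offs of one score (SAP 7.2.2). The correlation between F-VASI, T-VASI and VNS is not in the documents; it is assumed and varied.

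**Step 1: reproduce the printed powers.** The arcsine approximation to Fisher's test (Walters) is

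power = Φ{2[asin√(p₁ − 1/(2n₁)) − asin√(p₂ + 1/(2n₂))] × √(n₁n₂/(n₁+n₂)) − 1.96}, with √(200 × 100/300) = 8.165.

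| Rates | Printed | Arcsine | Exact enumeration |
|---|---|---|---|
| 20% v 5% | 95% | 95.5% | 96.6% |
| 30% v 10% | 95% | 98.1% | 98.6% |
| 10% v 1% | 88% | 88.9% | 92.0% |

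The 95% for F-VASI75 and the 88% rows are therefore single-test powers, matched within one point by the approximation. The F-VASI50 value is understated. Every binary endpoint exceeds 85% when tested alone.

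**Step 2: define cumulative power.** For step k it is P(tests 1 to k all succeed). If T-VASI50 and VNS were independent of F-VASI and of each other, it could be found by hand from the nested F-VASI result of 89.5% (step 3):

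- T-VASI50: 0.895 × 0.920 = 0.823
- VNS: 0.823 × 0.920 = 0.757

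**Step 3: allow for nesting and correlation.** Trials of 200 v 100 were simulated (100,000 per correlation). One latent normal F-VASI score per participant was cut at the planned rates to give the three nested responses. Separate latent T-VASI and VNS scores had common within-arm correlation ρ with it and with each other. Fisher's exact test was applied at each step, stopping at the first failure. The F-VASI steps do not depend on ρ: 96.7%, 96.0% and 89.5%.

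| ρ | T-VASI50 | VNS |
|---|---|---|
| 0 | 82.2% | 75.5% |
| 0.3 | 82.6% | 76.4% |
| 0.5 | 83.1% | 77.4% |
| 0.7 | 83.8% | 78.9% |
| 0.9 | 85.1% | 81.8% |
| 0.95 | 85.8% | 83.1% |
| 0.98 | 86.6% | 84.7% |

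The ρ = 0 row agrees with the hand calculation. Separate runs agreed within one point, and VNS reached about 85% only near ρ = 0.99.

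**Step 4: F-BSA.** It is tested only if VNS succeeds, so its cumulative power cannot exceed the VNS column.

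**The case against.** **The tables are valid as they stand.** The footnote shows that each figure is a single Fisher test at 0.05, and neither document claims joint power. This stands: it is an omission in how power is stated, not a miscalculation. It does not rescue the sentence in 10.1, which presents > 85% as the power for endpoints that the same protocol tests only in sequence.

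**The T-VASI50 gap is small.** It is 0 to 3 points and disappears at a correlation of about 0.9. This stands. T-VASI includes the face and VNS is rated on the face, so positive correlation is likely and the low end of each range is the least credible. VNS nevertheless stays below 85% until the correlation is almost 1.

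**The planning rates are cautious.** Protocol 2.4.2.2.3 reports Phase 2 rates at 1.5% BID v vehicle of 30.3% v 0% (F-VASI75), 45.5% v 3.1% (F-VASI50) and 12.1% v 0% (T-VASI50). With those rates, vehicle F-VASI75 set to 1%, and 10% v 1% kept for F-VASI90 and VNS, cumulative power is about 92% for T-VASI50 and 85% to 87% for VNS. With vehicle F-VASI90 at 0%, VNS is about 92%. So the shortfall is a statement about the planning rates. That is the right basis for checking a power claim made at those rates, and the readable text gives no Phase 2 rate for F-VASI90 or VNS.

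**Stronger readings a reader might infer.** One is to multiply the printed powers: 0.95 × 0.95 × 0.88 × 0.88 × 0.88 = 0.615, or about 62% for VNS. This treats F-VASI50, 75 and 90 as independent when they are cut-offs of one score, so it should not be used. Another is that the error rate is not controlled or the trial is too small for its primary aim. The documents support neither: the fixed sequence controls Type I error, and the three F-VASI steps stay above 85%.

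**Conclusion.** The point holds as a power statement that omits the testing sequence. At the plan's own rates, VNS falls about 3 to 9 points short of the stated 85% (76% to 82%). F-BSA has no figure and can do no better. T-VASI50 is borderline at 82% to 85%. F-VASI75, F-VASI50 and F-VASI90 meet the target through the sequence (about 97%, 96% and 89%).

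The ranges rest on an assumed latent correlation of 0 to 0.9, on full 200 v 100 data with no loss, and on Fisher's test as the plan uses it for power. They start from the exact 92.0% for the 10% v 1% endpoints, which favours the plan; starting from the printed 88% would lower them. The primary endpoint and the validity of the tests are unaffected.

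**What to change.** Keep the sample size and the test order. In Protocol 10.1 and SAP 3.3:

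1. Label Table 14 and SAP Table 2 as per-endpoint power.
2. Add a column of cumulative power under the fixed sequence, with the assumed correlation range stated. On the assumptions above it would read about 97%, 96%, 89%, 82% to 85% and 76% to 82%. Add a note that F-BSA cannot exceed the VNS value.
3. Reword the sentence so that > 85% applies to each binary endpoint tested on its own. State that, through the sequence, power is below 85% for VNS and F-BSA and about 85% or slightly less for T-VASI50.

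The cost is a wording and table change in two documents and less favourable printed figures; no participants are added. For scale only, reaching about 86% to 89% for VNS through the sequence on the same assumptions would take about 345 participants (230 v 115). The correction does not require this.

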10.2. Populations for Analysis

The populations for analysis are presented in [Table 15](#).

Table 15: Populations for Analysis

Population	Description
ITT	The ITT population includes all randomized participants. Treatment groups for this population will be defined according to the treatment assignment at randomization.
PP	The PP population includes randomized participants who are considered to be sufficiently compliant with the Protocol.
Safety	The safety population includes all participants who applied at least 1 dose of study drug. Treatment groups for this population will be determined according to the actual treatment the participant received on Day 1.
PK/ pharmacodynamic evaluable	The PK/pharmacodynamic evaluable population includes participants who applied at least 1 dose of ruxolitinib cream and provided at least 1 postdose blood sample for PK. The study pharmacokineticist will review data listings of participant administration and sample records to identify participants to be excluded from the analysis.

10.3. Statistical Analyses

The Statistical Analysis Plan will be developed and finalized before database lock and will describe the details of the statistical analyses and procedures for accounting for missing data. This section is a summary of the planned statistical analyses of the primary and secondary endpoints.

The gatekeeping testing strategy for the primary and key secondary analyses will be implemented to control the overall Type I error rate, 2-sided $\alpha = 0.05$. These endpoints will be tested in a fixed sequence at 2-sided $\alpha = 0.05$ level in the following order:

- Proportion of participants achieving F-VASI75 at Week 24
- Proportion of participants achieving F-VASI50 at Week 24
- Proportion of participants achieving F-VASI90 at Week 24
- Proportion of participants achieving T-VASI50 at Week 24
- Vitiligo - VNS Response at Week 24
- Percentage change from baseline in F-BSA at Week 24

10.3.1. Efficacy Analyses

10.3.1.1. Primary Analysis

The primary analysis will be based on the intent-to-treat population. The primary alternative hypothesis (superiority of ruxolitinib cream 1.5% BID compared with vehicle) will be tested using exact logistic regression ([Mehta and Patel 1995](#)). This model will include the treatment group (1.5% BID and vehicle) and stratification factors. The p-value for between-treatment

group testing will be compared with 0.05. Odds ratio and corresponding 95% confidence interval will be provided for comparing ruxolitinib cream and vehicle group at Week 24.

All nonresponders in the double-blind treatment period, as well as all participants who discontinue study treatment at any time before the timepoint of interest, or discontinue from the study for any reason, will be defined as nonresponders for the nonresponder imputation analysis.

Analysis will also be performed in the PP population for the primary endpoint. The following deviations are considered major:

- Missing primary endpoints on F-VASI;
- Compliance less than 60% based on the application numbers.

Participants with 1 or more such deviations will be excluded from the PP population. In addition, Protocol deviations related to inclusion/exclusion criteria, discontinuation criteria, and use of excluded concomitant medications will be evaluated and decided whether they should be excluded. Any exclusion from the PP population will be decided prior to breaking the blind.

In addition, sensitivity analyses, including MI and LOCF, may be performed. For MI, a fully conditional specification method ([van Buuren et al 2007](#)) that assumes the existence of a joint distribution for all variables will be used to impute F-VASI scores. A regression model including treatment group, stratification factors, and baseline and postbaseline F-VASI scores up to Week 24 will be specified for the fully conditional specification method. After the missing values are imputed, the binary variables will be derived based on the definition. The randomization seed will be set to 18424307 and the imputation will be repeated 10 times to generate corresponding complete data sets, in order to reflect the uncertainty around the true value. Exact logistic regression will be applied to each imputed dataset, and then the results will be combined for the inference. For LOCF, for the participants who discontinue study treatment at any time before the timepoint of interest or discontinue from the study for any reason, the last observed nonmissing value will be used to fill in missing values at the timepoint of interest. A tipping point analysis will be conducted to examine the potential effects of missing data. The missing binary response on F-VASI75 at Week 24 in each treatment group will be replaced by a range of values from the most conservative case to the most aggressive case. The most conservative case is that all the missing participants in active treatment groups are nonresponders and all the missing participants in the placebo group are responders, while the most aggressive case is the other way around. For each scenario, between-treatment comparisons will be performed using a chi-square test.

Subgroup analysis by baseline character, for example, skin type, age, and region, will be performed. Details will be provided in the Statistical Analysis Plan.

10.3.1.2. Key Secondary Analysis

If the primary objective is achieved, the statistical hypotheses for key secondary endpoints will be tested in the frequency specified in Section [10.3](#).

Key secondary efficacy analyses at Week 24 will be conducted in the ITT population. The statistical comparisons for binary outcomes (VASI50/90 and VNS response) will be analyzed using the similar method as specified in the primary analysis. For F-BSA, the missing values at Week 24 will be imputed using the similar multiple imputation method specified in the primary

analysis. Then the derived percentage change from baseline in F-BSA at Week 24 will be analyzed using an ANCOVA model with treatment group, stratification factors, and baseline value as covariates. A test for superiority between INCB018424 1.5% BID and vehicle cream will be performed using the least squares mean estimate of the percentage change from baseline in F-BSA at Week 24 from the ANCOVA model specified above. Superiority will be established if the p-value of the difference (INCB018424 1.5% BID minus vehicle) is less than 0.05.

